
 
To evaluate the persistence of the immune response to mRNA-1273 vaccine (25, 50, and 100 <math>\mu</math>g)
 
	
 
The GM values of SARS-CoV-2 S protein-specific bAb on Day 1, Day 57 (1 month after Dose 2), Day 209 (6 months after Dose 2), Day 394 (1 year after Dose 2), BD-Day 1 (at least 3 months or 6 months after Dose 2), BD-Day 29 (1 month after booster dose or third dose), BD-Day 181 (6 months after booster dose or third dose), and BD-Day 366 (1 year after booster dose or third dose)
 
The GM values of SARS-CoV-2-specific nAb on Day 1, Day 57 (1 month after Dose 2), Day 209 (6 months after Dose 2), Day 394 (1 year after Dose 2), BD-Day 1 (at least 3 months or 6 months after Dose 2), BD-Day 29 (1 month after booster dose or third dose), BD-Day 181 (6 months after booster dose or third dose), and BD-Day 366 (1 year after booster dose or third dose)
 

 
To evaluate the incidence of SARS-CoV-2 infection after vaccination with mRNA-1273 or placebo
 
	
 
The incidence of SARS-CoV-2 infection including symptomatic and asymptomatic infection (by serology and/or RT-PCR) postbaseline
 
SARS-CoV-2 infection will be defined in participants with negative SARS-CoV-2 at baseline: 
 
bAb level against SARS-CoV-2 nucleocapsid protein negative at Day 1, that becomes positive (as measured by Roche Elecsys) postbaseline, OR
 
Positive RT-PCR postbaseline
 
 
 

 
To evaluate the incidence of asymptomatic SARS-CoV-2 infection after vaccination with mRNA-1273 or placebo
 
	
 
The incidence of SARS-CoV-2 infection measured by RT-PCR and/or bAb levels against SARS-CoV-2 nucleocapsid protein (by Roche Elecsys) postbaseline in participants with negative SARS-CoV-2 at baseline, in the absence of any COVID-19 symptoms
 

Objectives	Endpoints

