- Participant unblinds and has received placebo:
  - Participant will have 2 options:

1. Discontinue participating in the KidCOVE study
2. Cross-over to mRNA-1273 (following [Table 13](#)- through Day 57 safety follow-up call)
  - A pregnancy test should be done for participants that are post-menarche prior to Dose 1 and Dose 2.
  - For the remainder of the study visits, as noted in [Table 13](#), the participants will be followed for MAAEs, SAEs, and AESIs and concomitant medication relevant to, or for the treatment of MAAEs and SAEs.
  - Participants will continue being followed for safety, which includes COVID-19 surveillance, using electronic eDiaries and safety follow-up calls that will continue to trigger from the participant's original (placebo) administration date.
  - Participants will have a clinic visit at study Day 209 from the original (placebo) administration date. At this visit, they will have a symptom-directed physical exam, if necessary, illness visit or convalescent visit work-up, if applicable, and a nasal swab. No blood samples will be required for this visit.
  - Participants will have a clinic visit at study Day 394 from the original (placebo) administration date. At this visit, they will have a symptom-directed physical exam, if necessary, illness visit or convalescent visit work-up, if applicable, and a nasal swab.

In summary: No immunogenicity or serology samples will be required for cross-over participants unless they are part of a convalescent visit work-up or if they choose to receive a booster dose (as per [Table 15](#), they will require a BD-Day1 baseline blood draw.)

**Table 14: Phlebotomy Schedule for Serology, Biomarker Sample, and Cell-Mediated Immunity for Part 2 (Expansion) of the Study**

**For participants that chose to receive a booster dose under protocol Amendment 7, please see [Table 16](#) for the booster dose phlebotomy schedule.**

**If Day 209/Day 394 blood draw is within 30 days of planned BD-Day 1, BD-Day 1 blood draw can be used for Day 209/Day 394.**

Cohort	Number of Subjects		Study Visit Day					
		D1 	D29 	D30 (+3) 	D43	D57	D209 (+30 days) 	D394 (+30 days) 
Phlebotomy Schedule for Serology: To be Executed Within Age Group								
A	First 176 (132 mRNA-1273: 44 placebo)	X	X			X		
B	Next 176 (132 mRNA-1273: 44 placebo)	X				X	X	
C	Next 176 (132 mRNA-1273: 44 placebo)	X				X		X
D	Remainder of the age group	X		X 				

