Phlebotomy Schedule for Cell-Mediated Immunity: To be Executed Within Each Age Group at Selected VTEU Sites only								
E (CMI with exploratory serology)	24 (18 mRNA-1273: 6 placebo)	X			X		X	X

Abbreviations: BD = booster dose; CMI = cell-mediated immunity; D = day; mRNA = messenger RNA; VTEU = Vaccine and Treatment Evaluation Units.

. On Day 1, sample must be collected prior to randomization and dosing. On Day 29, sample must be collected prior to dosing.

. If a Day 1 (baseline) blood sample cannot be obtained in either Part 1 or Part 2, the participant will be considered either a screen failure due to inability to satisfy inclusion criterion 3 or could be scheduled for rescreening. Participants may be rescreened 1 time, either within same screening period for Part 1 or Part 2 or in a new screening period for Part 2 if the initial screening was in Part 1. If the participant is rescreened and a blood sample still cannot be obtained, then he/she will be considered a screen failure due to inability to satisfy inclusion criterion 3.

. Serum sample from ~4 ml of blood only, to be stored for potential future use for biomarker assessment.

. If the participant decides to receive a booster dose, the BD1 blood draw ([Table 15](#)) can be used for Day 209 or Day 394 ([Table 14](#)).

**Table 15: Schedule of Assessments for Optional Booster Doses with mRNA-1273 for Parts 1 and 2, Study Arms 1 Through 9 under Protocol Amendment 7**

Visit Number	BD-1	BD-2	BD-2A	BD-3			BD-4	BD-5	BD-6
Type of Visit	C	SC	C	C	SFU		C	SC	C
Study Visit Day	BD-D1 	7 days after BD-D1 (BD-D8)	14 days after BD-D1 (Sub-Cohort E only and optional) BD-D15	BD-D29	eDiary	SC			
Window Allowance (Days)	0	+ 3	+ 3	-3/+14	± 3	± 3	-3/+14	+ 3	-3/+14
Days Since Most Recent Vaccination	0	7	14	28			180	270	365
Confirm informed consent /assent form booster addendum signing	X								
Physical examination 	X			X			X		X
Pregnancy testing 	X								
Immunogenicity Assessment									
Pre-booster blood for immunologic analysis  (or CMI with exploratory serology, as applicable) 	X								
Post-booster blood for immunologic analysis (or CMI with exploratory serology, as applicable) 			X	X			X		X
Dosing									
Study injection (including 30-minute post-dosing observation period) 	X								
Unscheduled Visits 	X	X	X	X	X	X	X	X	X
Nasal swab 	X			X			X		

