Safety Assessments									
Follow-up safety call 		X						X	

Visit Number	BD-1	BD-2	BD-2A	BD-3	SFU		BD-4	BD-5	BD-6
Type of Visit	C	SC	C	C	SFU		C	SC	C
Study Visit Day	BD-D1 	7 days after BD-D1 (BD-D8)	14 days after BD-D1 (Sub-Cohort E only and optional) BD-D15	BD-D29	eDiary	SC			
Window Allowance (Days)	0	+ 3	+ 3	-3/+14	± 3	± 3	-3/+14	+ 3	-3/+14
Days Since Most Recent Vaccination	0	7	14	28			180	270	365
eDiary activation for recording solicited ARs (7 days) 	X								
Review of eDiary data 		X		X					
Recording of unsolicited AEs, concomitant medications and nonstudy vaccinations	X	X	X	X					
Recording of AE leading to withdrawal and concomitant medications relevant for AE leading to withdrawal	X	X	X	X	X	X	X	X	X
Recording of SAEs, AESI and MAAEs and concomitant medications relevant to or for the treatment of the SAE, AESI or MAAE 	X	X	X	X	X	X	X	X	X

Abbreviations: AE = adverse event; AESI = adverse event of special interest; AR = adverse reaction; BD = booster dose; C = clinic visit; CMI = cell-mediated immunity; COVID-19 = coronavirus disease 2019; D = day; eDiary = electronic diary; FDA = Food and Drug Administration; MAAE = medically attended AE; mRNA = messenger RNA; RT-PCR = reverse transcriptase polymerase chain reaction; SAE = serious adverse event; SARS-CoV-2 = severe acute respiratory syndrome coronavirus 2; SC = safety (phone) call; SFU = safety follow up.

Note: In accordance with FDA Guidance on Conduct of Clinical Trials of Medical Products during COVID-19 Public Health Emergency (DHHS 2020), investigators may convert study site visits to home visits or telemedicine visits with the approval of the Sponsor.

1. A BD may be administered to Part 1 participants (all ages) and 6 to < 12 year old Part 2 participants provided there are no current contraindications for further dosing. A participant who is currently in the Convalescent Period may come in for a BD-1 visit and receive a BD as long they are at least 90 days from initial diagnosis of COVID-19. Applicable participants will be offered a booster at least 6 months (Participants in part 1 and participants 6 to < 12 year old in Part 2) after Dose 2.

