Abbreviations: AE = adverse event; AESI = adverse event of special interest; AR = adverse reaction; BD = booster dose; C = clinic visit; CMI = cell-mediated immunity; COVID-19 = coronavirus disease 2019; D = day; eDiary = electronic diary; FDA = Food and Drug Administration; MAAE = medically attended AE; mRNA = messenger RNA; RT-PCR = reverse transcriptase polymerase chain reaction; SAE = serious adverse event; SARS-CoV-2 = severe acute respiratory syndrome coronavirus 2; SC = safety (phone) call; SFU = safety follow up.

Note: In accordance with FDA Guidance on Conduct of Clinical Trials of Medical Products during COVID-19 Public Health Emergency (DHHS 2020), investigators may convert study site visits to home visits or telemedicine visits with the approval of the Sponsor.

1. A BD may be administered to all Part 2 participants provided there are no current contraindications for further dosing and have not received any booster doses outside of the trial. A participant who is currently in the Convalescent Period may come in for a BD-1 visit and receive a BD as long they are at least 90 days from initial diagnosis of COVID-19. Applicable participants will be offered a booster at least 3 months after Dose 2.
2. Symptom-directed physical examination will be performed at the BD-D1. On dosing day before injection, the arm receiving the injection should be examined and the associated lymph nodes should be evaluated. At visits BD-3 (BD-D29), BD-4 (BD-D181) and BD-6 (BD-D366), a symptom-directed

physical examination may be performed at the discretion of the investigator. Any clinically significant finding identified during a study visit should be reported as a MAAE. An oral or tympanic temperature should be taken on the day of injection (BD-D1) prior to dosing. Participants who are febrile (body temperature  $\geq 38.0^{\circ}\text{C}/100.4^{\circ}\text{F}$ ) before dosing (BD-D1) must be rescheduled to receive the injection. Afebrile participants with minor illnesses can be vaccinated at the discretion of the investigator.

3. Pregnancy test at BD-D1 before the booster dose injection will be a point-of-care urine test and will be performed if deemed appropriate by the investigator. At the discretion of the investigator, a pregnancy test either via blood or point-of-care urine test can be performed at any time during the study.
4. Sample should be collected prior to dosing on BD-D1.

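### Table 14 footnote 4 lets the pre-booster draw stand in for Day 209 or Day 394 with no time limit, contradicting the 30-day condition in the same table, and the draw windows for these two days also disagree

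*Protocol*

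**What the plan says.** Section 2, Table 2 makes the geometric mean (GM) of binding and neutralizing antibody a secondary persistence endpoint at named times. These include Day 209 (6 months after Dose 2), "Day 394 (1 year after Dose 2", and, as a separate time, "BD-Day 1 (at least 3 months or 6 months after Dose 2".

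Four statements in Section 10.1 (Appendix 1) govern the Day 209 and Day 394 samples in Part 2:

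- **Table 12** gives both visits a window of ±14 days.
- **Table 14, column heads**, give both draws +30 days, with no early allowance.
- **Table 14, bold note at the head**, sets a condition for using the pre-booster draw instead: "If Day 209/Day 394 blood draw is within 30 days of planned BD-Day 1".
- **Table 14, footnote 4**, attached to both columns, repeats the substitution without that condition: "If the participant decides to receive a booster dose, the BD1 blood draw" of Table 15 "can be used for Day 209 or Day 394".

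Table 15, footnote 1 sets a minimum booster interval and no maximum: "Applicable participants will be offered a booster at least 6 months" after Dose 2.

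**The concern.** A site following footnote 4 may skip the scheduled Day 394 draw and enter a pre-booster sample taken months earlier in its place. A site following the note may not. Titers are expected to fall after Dose 2, so an early sample carrying the 1-year label makes the response look more durable than it is. The same sample is also the BD-Day 1 sample, so it could be counted at two time points of one endpoint.

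Cohort C is the most exposed. Day 394 is its only late persistence draw, and Table 16 gives a boosted Sub-Cohort C child only BD-Day 29 afterwards. The BD-Day 1 draw is therefore the child's last sample before boosting. A scheduled draw that was never taken cannot be recovered at analysis.

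**Working it through.** **Nominal times.** Dose 2 is on Day 29. Then 209 − 29 = 180 days and 394 − 29 = 365 days, which reproduces the days since last injection printed in Table 12.

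**Windows, in study days.**

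| Source | Rule | Day 209 | Day 394 |
|---|---|---|---|
| Table 12 | ±14 days | 195 to 223 | 380 to 408 |
| Table 14 column heads | +30 days | 209 to 239 | 394 to 424 |
| Table 14 bold note | within 30 days | 179 to 239 | 364 to 424 |
| Table 14 footnote 4 | none stated | from the earliest booster | from the earliest booster |

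No two rows agree. The bold note admits early samples that the column heads exclude.

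**Earliest substitute under footnote 4.** The footnote points to Table 15, where the minimum interval is 6 months. Taking 6 months as 180 to 183 days, the earliest BD-Day 1 is 29 + 180 = Day 209 to 29 + 183 = Day 212. Against Day 394 this is 394 − 209 = 185 to 394 − 212 = 182 days early. Against Day 209 it is 0 to 3 days late, so Day 209 cannot be read materially early.

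**Earliest substitute under the bold note.** 394 − 30 = Day 364, at most 30 days early.

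**Does the choice of rule matter in practice?** Cohorts A to C fill before Cohort D, and the Table 16 dates for Sub-Cohort D begin on 11 Aug 2021, so Cohort C was probably enrolled by about then (an inference). For a child enrolled on that date:

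- Amendment 7 (18 Feb 2022), which introduced the mRNA-1273 booster, falls on Day 192.
- Amendment 9 (04 Aug 2022), which replaced it, falls on Day 359.
- 394 − 359 = 35 days, so the whole period lies more than 30 days before Day 394.

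Earlier enrollment raises these day numbers by the same number of days, and amendment dates are not site start dates. With those caveats, most BD-Day 1 draws under Amendment 7 would count as Day 394 samples under footnote 4 and not under the note.

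**Size.** The protocol gives no decay rate. Assume a half-life h of 60 to 200 days. A sample taken k days early is too high by a factor of 2^(k/h):

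- k = 30 (the note's limit): 2^(30/200) = 1.11 to 2^(30/60) = 1.41.
- k = 94 (drawn on Day 300): 2^(94/200) = 1.39 to 2^(94/60) = 2.96.
- k = 154 (drawn on Day 240): 2^(154/200) = 1.71 to 2^(154/60) = 5.92.

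These are per-sample factors. If a fraction f of the cohort's samples is substituted at the same k, the GM is inflated by the factor raised to the power f. The documents do not give f.

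**Who is exposed.** Table 14 covers Part 2 only. Under Table 15, the Part 2 participants offered the booster are those aged 6 to <12 years. That leaves Cohort C of that age group (132 mRNA-1273 recipients) and the Day 394 exploratory serology of Cohort E (18 mRNA-1273 recipients).

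**The case against.** The strongest reply is that the bold note and footnote 4 belong to one table and should be read together: the note sets the condition and the footnote only identifies the draw. On that reading the 6-month figure does not arise. This is a reasonable reading, but the footnote states its own condition (that the participant decides to have a booster) and sits on the two columns that a site consults. The text does not say which rule prevails.

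It can also be said that Table 12 sets visit windows and Table 14 sets draw windows. But Table 12 also schedules the Part 2 immunogenicity sample at those visits, so both apply to the same blood.

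A further reply is that Section 7.2 records the date and time of each sample, that BD-Day 1 has its own label in the endpoint, and that assigning samples to analysis visits is normal SAP content. This stands and limits the harm. It does not settle whether a site must still take the scheduled draw.

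Several stronger readings are tempting and are not supported:

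- *That a draw at any time may be used, so the 1-year GM is about 6 months early.* The note contradicts this, and even footnote 4 alone starts at 6 months after Dose 2. The 185 days is a worst case for one sample.
- *That Amendment 9 boosters widen the gap.* Table 19 says "Applicable participants will be offered a booster at least 3 months after Dose 2", but footnote 4 refers to Table 15, not Table 19.
- *That Day 209 is distorted to a similar degree.* It could only be read late, and Section 5.4 classes a visit not completed in its window as missed.
- *That every age group is affected.* The Table 15 booster reaches only the 6 to <12 group in Part 2.

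**Conclusion.** The contradiction is real and lies in current operative text. The error in a substituted Day 394 sample is at most 30 days if the note governs and up to about 185 days if footnote 4 governs. The day counts rest only on the protocol's own schedule. The fold-errors rest on an assumed half-life and are illustrative, and the effect on the cohort GM cannot be stated without the share of children boosted early. The direction, overstatement of 1-year persistence, follows from waning.

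The consequence is moderate. The endpoint is secondary and is summarized descriptively as a GM with a 95% CI (Section 8.5.3). No hypothesis, multiplicity step or power figure depends on it. It should still be corrected, because the two rules decide differently for most boosters given under Amendment 7 and the correction is cheap.

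**What to change.** 1. Add the note's 30-day limit to Table 14 footnote 4, or delete the footnote and let the note stand alone.
2. State one blood-draw window for Day 209 and one for Day 394, identical in Tables 12 and 14 and consistent with the substitution rule.
3. Report BD-Day 1 draws outside that window only as BD-Day 1, or by actual days since Dose 2 from the recorded sample dates, and never under a nominal Day 209 or Day 394 label.

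A mixed model of log titer on time since Dose 2 would make use of the out-of-window samples, but it is optional.

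The cost is one footnote, one window entry and a line on sample labelling. No further samples are needed. The downside is that some draws no longer count toward a nominal visit, so the Day 394 GM may rest on fewer children.

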**Table 17: Schedule of Assessments for Part 3, Study Arm 14**

Visit Number	0	1	2	3	4	5			6	6A	6B			7	8
Type of Visit	C	C	TMV	C	TMV	C	SFU		C	TMV	C	SFU		C	C
Month Time Point		M0		M1		M2	eDiary	SC	M5		M6	eDiary	SC	M11	M17
Study Visit Day															
Window Allowance (Days)	-	-	+ 3	+ 7	+ 3	+ 7	± 3	± 3	± 28	+ 3	+ 7	± 3	± 3	± 14	± 14
Days Since Most Recent Injection	-	0	7	28	7	28	-	-	120/0	127/7	148/28	-	-	305/ 180	485/ 365
Informed consent/assent form, demographics, concomitant medications, medical history	X														
Review of inclusion and exclusion criteria	X	X								X					
Physical examination including body temperature, length/height, weight, and BMI 	X	X		X		X			X					X	X
Pregnancy test 	X	X		X					X						
Randomization		X													
Study injection (including 30-minute post-dose observation period)		X		X					X						
Blood sample for vaccine immunogenicity (Part 3) 		X			X				X 		X			X 	X 
Nasal swab sample for SARS-CoV-2 	X		X		X				X		X			X	X
Unscheduled visit 		X	X	X	X	X	X	X	X	X	X	X	X	X	X
eDiary activation for recording solicited ARs (7 days) 	X		X						X						
Review of eDiary data			X		X					X					
Follow-up safety telephone calls 								X		X			X		
Recording of unsolicited AEs		X	X	X	X	X				X	X	X			

Visit Number	0	1	2	3	4	5			6	6A	6B			7	8
Type of Visit	C	C	TMV	C	TMV	C	SFU		C	TMV	C	SFU		C	C
Month Time Point		M0		M1		M2	eDiary	SC	M5		M6	eDiary	SC	M11	M17
Study Visit Day	D-28 to D-1 (Screening) 	D1 (Baseline)	D8	D29 	D36 	D57 	Every 4 weeks D71 – D183 	Every 4 weeks D85 – D197 	D149 (BD-D1)	D156 (BD-D8)	D177 (BD-D29)	Every 4 weeks D191 (BD-D43) – D303 (BD-155) 	Every 4 weeks D205 (BD-D57) – D317 (BD-D169) 	D329 (BD -D181) 	D514 (BD-D366)
Window Allowance (Days)	-	-	+ 3	+ 7	+ 3	+ 7	± 3	± 3	± 28	+ 3	+ 7	± 3	± 3	± 14	± 14
Days Since Most Recent Injection	-	0	7	28	7	28	-	-	120/0	127/7	148/28	-	-	305/ 180	485/ 365
Recording of MAAEs, SAEs, and AESIs (eg, MIS-C, myocarditis/pericarditis) and concomitant medications and procedures relevant to or for the treatment of the MAAE, AESI and SAE 	X	X	X	X	X	X	X	X	X	X	X	X	X	X	X
Recording of concomitant medications and procedures and nonstudy vaccinations 	X	X	X	X	X				X	X	X				
Study completion															X

Abbreviations: AE = adverse event; AESI = adverse event of special interest; AR = adverse reaction; BD = booster (third) dose; BMI = body mass index; C = clinic visit; COVID-19 = coronavirus disease 2019; D = day; eCRF = electronic case report form; EDC = electronic data capture; eDiary = electronic diary; FDA = Food and Drug Administration; IP = investigational product; IRB = institutional review board; LAR = legally authorized representative; M = month; MAAE = medically attended adverse event; MIS-C = multisystem inflammatory syndrome in children; RT-PCR = reverse transcriptase polymerase chain reaction; SAE = serious adverse event; SARS-CoV-2 = severe acute respiratory syndrome coronavirus 2; SC = safety (telephone) call; SFU = safety follow-up; TMV = telemedicine visit.

**Note:** In accordance with FDA Guidance on Conduct of Clinical Trials of Medical Products during COVID-19 Public Health Emergency (FDA March 2020), investigators may convert study site visits to home visits or telemedicine visits (with the exception of Screening, Day 1, Day 29, and Day 149) with the approval of the Sponsor.

1. Screening Visit and Day 1 may be combined on the same day. Additionally, the Screening Visit may be performed over multiple visits if performed within the 28-day screening window.
2. If the visit for the second dose (Day 29) is disrupted and cannot be completed at Day 29 (+7 days) as a result of the COVID-19 pandemic (self-quarantine or disruption of study site activities following business continuity plans and/or local government mandates for “stay at home” or “shelter in place”), the visit window may be extended to Day 29 + 21 days. When the extended visit window is used, the remaining study visits should be

rescheduled to follow the intervisit interval from the actual date of the second dose. Refer to [Section 6.1.1](#) for individual participant criteria for delay of study vaccination.

- 3. All scheduled study visits should be completed within the respective visit windows. If the participant is not able to attend a study site visit as a result of the COVID-19 pandemic (self-quarantine or disruption of study site activities following business continuity plans and/or local government mandates for “stay at home” or “shelter in place”), a telemedicine visit should be conducted in place of the study site visit. The telemedicine visit should encompass all scheduled visit assessments that can be completed remotely, such as assessment for AEs and concomitant medications (eg, as defined in scheduled safety telephone calls). Home visits will be permitted for all nondosing visits, with the exception of Screening, if a participant cannot visit the study site as a result of the COVID-19 pandemic. Home visits must be permitted by the study site IRB and the participant’s parent(s)/LAR(s) via informed consent and have prior approval from the Sponsor (or its designee).
- 4. Safety follow-up via an eDiary questionnaire will be performed every 4 weeks from Day 71 to Day 183 and again from Day 191 to Day 303.
- 5. Safety follow-up via a safety telephone call will be performed every 4 weeks from Day 85 to Day 197 and again from Day 205 to Day 317.
- 6. A full physical examination, including body temperature (oral [for participants > 4 years of age] or tympanic [for participants ≤ 4 years of age]), length/height, and weight, will be performed at the Screening Visit or on Day 1. Symptom-directed physical examination will be performed on Day 1, Day 29, Day 57, Day 149, Day 329, and Day 514 and may be performed at other time points at the discretion of the investigator. Body mass index will be calculated only at Screening Visit. Body temperature (oral/tympanic) should be measured on each injection day prior to injection. On each injection day before injection and again 7 days after injection, the injection site should be examined. Any clinically significant finding identified during a study visit should be reported as an MAAE. Participants who are febrile (body temperature ≥ 38.0°C/≥ 100.4°F) before injection on Day 1 Day 29, or Day 149 must have the visit rescheduled within the relevant visit window to receive the injection. Afebrile participants with minor illnesses may be injected at the discretion of the investigator.
- 7. Pregnancy test at Screening and Day 1 and before the second and third study injection will be a point-of-care urine test and will be performed if deemed appropriate by the investigator. At the discretion of the investigator, a pregnancy test either via blood or point-of-care urine test can be performed at any time during the study.
- 8. On Day 1, sample must be collected prior to randomization and dosing. If a Day 1 (baseline) blood sample cannot be obtained in Part 3, the participant will be considered either a screen failure due to inability to satisfy inclusion criterion 3 or could be scheduled for rescreening. Participants may be rescreened 1 time. If the participant is rescreened and a blood sample still cannot be obtained, then he/she will be considered a screen failure due to inability to satisfy inclusion criterion 3.
- 9. On Day 149, sample must be collected prior to dosing.
- 10. Sub-Cohort F only, see [Table 18](#) for details.
- 11. Sub-Cohort G only, see [Table 18](#) for details.
- 12. The nasal swab sample (collected before dosing on injection day) will be used to ascertain the presence of SARS-CoV-2 via RT-PCR.
- 13. An unscheduled visit may be prompted by reactogenicity issues, or new or ongoing AEs.
- 14. A convalescent visit may be scheduled approximately 28 days (+7 days) after diagnosis of COVID-19 if there are any doubts about initial diagnosis (at investigator’s discretion). At this visit, a blood sample for potential immunologic assessment of SARS-CoV-2 infection will be collected.
- 15. At each injection visit, participants’ parent(s)/LAR(s) will record data into the eDiary starting approximately 30 minutes after injection under the supervision of the study site staff to ensure successful entry of assessment. Participants’ parent(s)/LAR(s) will continue to record entries in the eDiary after they leave the study site, preferably in the evening and at the same time each day, on the day of injection and for 6 days following injection. If a solicited local or systemic AR continues beyond Day 7 after vaccination, the participant’s parent(s)/LAR(s) will be prompted to capture details of the solicited local or systemic AR in the eDiary until the AR is resolved or the next IP injection occurs, whichever occurs first. Capturing details of ARs in the eDiary should not exceed 28 days after each vaccination. Adverse reactions recorded in eDiaries beyond Day 7 should be reviewed by the study site staff either during the next scheduled telephone call or at the next study site visit.

16. Trained study site personnel will call all participants to collect information relating to any MAAEs, SAEs, AEs leading to study withdrawal and information on concomitant medications associated with those events and any nonstudy vaccinations. In addition, study personnel will collect information on known participant exposure to someone with known COVID-19 or SARS-CoV-2 infection and on any COVID-19 symptoms the participant may experience.
17. All concomitant medications and procedures and nonstudy vaccinations will be recorded through 28 days after each injection; all concomitant medications relevant to or for the treatment of an SAE, AESI or MAAE will be recorded from Day 1 through the final visit (Day 514).
18. In addition to MIS-C and myocarditis and/or pericarditis, a list of AESIs pertinent to this study may be referenced in the list of AESIs that is maintained by the Sponsor and provided to each investigator. All SAEs and AESIs will be reported to the Sponsor or designee immediately and in all circumstances within 24 hours of becoming aware of the event via the EDC system. If a site receives a report of a new SAE or AESI from a study participant or receives updated data on a previously reported SAE or AESI and the eCRF has been taken offline, then the site can report this information on a paper SAE or AESI form using the SAE Mailbox, the SAE Hotline, or the SAE Fax line ([Section 7.4.11](#)).

